3.8.3. Vital Signs and Body Weight

3.8.3.1. Vital Signs

Descriptive statistics for vital signs and changes from baseline values at each scheduled time point will be presented for the treatment period.

Vital sign values will be considered PCS if they meet both the observed-value criteria and the change-from-baseline criteria listed in [Table 7](#). The number and percentage of subjects with PCS postbaseline values will be tabulated. The percentages will be calculated based on the number of subjects with abnormal baseline values and at least one postbaseline assessment. The numerator will be the number of subjects with abnormal baseline values and at least one postbaseline PCS value. A supportive listing of subjects with PCS postbaseline values will be provided.

All vital signs will be presented in the subject data listing.

Table 7: Criteria for Potentially Clinically Significant (PCS) Blood Pressure or Pulse Rate

Parameter	Criteria
Supine Systolic Blood Pressure	≤ 90 and decrease ≥ 20 mm Hg ≥ 180 and increase ≥ 20 mm Hg
Supine Diastolic Blood Pressure	≤ 50 and decrease ≥ 15 mm Hg ≥ 105 and increase ≥ 15 mm Hg
Supine Heart Rate	≤ 50 and decrease ≥ 15 bpm ≥ 120 and increase ≥ 15 bpm

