3.8.2. Clinical Laboratory Parameters

Laboratory parameters will be presented in conventional (ie, US) units. Only scheduled laboratory parameters will be included in the summaries, unless specified otherwise. All laboratory data, including those collected at unscheduled visits, will be included in the listings.

Laboratory results including baseline and change from baseline for the Safety Population during the treatment period for chemistry and hematology parameters will be summarized by visit.

Clinical laboratory test values, scheduled or unscheduled, will be considered potentially clinically significant (PCS) if they meet PCS criteria listed in [Table 3](#). The number and

percentage of subjects who have postbaseline PCS clinical laboratory values will be summarized. The percentages will be calculated based on the number of subjects with abnormal baseline value and have at least one postbaseline assessment. All PCS values including baseline PCS values will be included in supportive listings.

Shift tables for selected fasting metabolic parameters (glucose, total cholesterol, low density lipoprotein [LDL], high density lipoprotein [HDL], triglycerides, and hemoglobin A1c [HbA1c]) and liver function tests will be presented. The criteria are summarized in [Table 4](#), [Table 5](#), and [Table 6](#).

Table 3: Criteria of Potentially Clinically Significant (PCS) Abnormality for Selected Analytes

Parameter	Criteria
Chemistry	
Albumin	<2 g/dL
Alkaline Phosphatase (U/L)	$\geq 3 \times \text{ULN}$
Alanine Aminotransferase (U/L)	$\geq 3 \times \text{ULN}$
Aspartate Aminotransferase (U/L)	$\geq 3 \times \text{ULN}$
Bilirubin, Total	$\geq 2.0 \text{ mg/dL}$
Blood Urea Nitrogen	$>30 \text{ mg/dL}$
Cholesterol, Random	$>400 \text{ mg/dL}$
Cholesterol, Fasting ^a	$\geq 240 \text{ mg/dL}$
Cholesterol, Fasting	Increase $\geq 40 \text{ mg/dL}$
Cholesterol, HDL Fasting	$<40 \text{ mg/dL}$
Cholesterol, HDL Fasting	Decrease $\geq 20 \text{ mg/dL}$
Cholesterol, LDL Fasting	$\geq 160 \text{ mg/dL}$
Cholesterol, LDL Fasting	Increase $\geq 30 \text{ mg/dL}$
Creatine Kinase (U/L)	$\geq 3 \times \text{ULN}$
Creatinine	$\geq 2.0 \text{ mg/dL}$
Glucose, Random	$<40 \text{ mg/dL}$ or $\geq 250 \text{ mg/dL}$
Glucose, Fasting	$<50 \text{ mg/dL}$ or $\geq 126 \text{ mg/dL}$
Glucose, Fasting	Increase $\geq 10 \text{ mg/dL}$
HbA1c	$\geq 5.7\%$
Potassium	$<3 \text{ mmol/L}$ or $>5.5 \text{ mmol/L}$
Lactate Dehydrogenase (U/L)	$>3 \times \text{ULN}$

Parameter	Criteria

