3.8.3.2. Weight and Body Mass Index

Weight (kg), BMI (kg/m^2) and waist circumferences (cm) (baseline and change from baseline) will be summarized using observed data. Absolute and percent change from baseline in body weight will be summarized.

Number and percentage of subjects with $\geq 7\%$ or $\geq 10\%$ weight gain from baseline based on the observed data will be summarized by visit. Subgroup analysis by region (US vs non-US) will be performed. In addition, number and percentage of subjects with weight change values considered as PCS occurring at any post-baseline visit will be summarized. Criteria for PCS are presented below in [Table 8](#). The percentages will be calculated relative to the number of subjects in the Safety Population with at least one post-baseline value. A supportive listing will be provided for subjects with PCS values.

Table 8: Criteria for Potentially Clinically Significant (PCS) Changes from Baseline in Body Weight

Parameter	Criteria
Body Weight	Decrease from Baseline $\geq 7\%$ Increase from Baseline $\geq 7\%$

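### SAP percentages for potentially clinically significant labs and vital signs rest on an undefined abnormal-baseline group, which excludes new vital-sign cases with a non-abnormal baseline and mismatches the lab ratio

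*SAP*

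**What the plan says.** **Vital signs (SAP 3.8.3.1).** The definition is "Vital sign values will be considered PCS if they meet both the observed-value criteria and the change-from-baseline criteria" in SAP Table 7. The denominator is given as "The percentages will be calculated based on the number of subjects with abnormal baseline values and at least one postbaseline assessment", and the numerator as "The numerator will be the number of subjects with abnormal baseline values and at least one postbaseline PCS value".

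**Laboratory values (SAP 3.8.2).** The section promises the number and "percentage of subjects who have postbaseline PCS clinical laboratory values will be summarized". The denominator follows: "The percentages will be calculated based on the number of subjects with abnormal baseline value and have at least one postbaseline assessment". There is no separate numerator sentence. The section also provides listings ("All PCS values including baseline PCS values will be included in supportive listings") and "Shift tables for selected fasting metabolic parameters" and for liver function tests.

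**Weight (SAP 3.8.3.2).** The same kind of PCS percentage is based on a different group: "The percentages will be calculated relative to the number of subjects in the Safety Population with at least one post-baseline value".

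**Protocol.** Section 14.6 and the synopsis plan the number and percentage of subjects meeting PCS criteria at any visit after baseline, for labs and vital signs. Neither mentions baseline status. SAP section 5 lists one change from the protocol, the CGI-S shift analysis.

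**The concern.** A PCS table in a long-term safety study is read as the share of subjects who reached a worrying value on treatment. Limiting it to subjects who were already abnormal at baseline answers a different question, and it removes the subjects of most interest: those who started in an acceptable range and then crossed the limit.

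The term is also undefined here. SAP Table 7 needs a change from baseline, so it cannot by itself classify a baseline value. SAP Tables 4 to 6 give baseline categories for nine analytes only. No vital-sign reference range appears in either document.

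Long-term safety is part of the primary objective. The study is descriptive and reported as one group, so these percentages are themselves a result, and no comparator would show that they are wrong.

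**Working it through.** The documents state no PCS rate, so there is no figure to reproduce. The check compares the definitions and works out what each can count.

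**1. Definitions side by side**

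| Analysis | Numerator | Denominator |
|---|---|---|
| Vital signs, SAP 3.8.3.1 | abnormal baseline and a postbaseline PCS value | abnormal baseline and a postbaseline assessment |
| Labs, SAP 3.8.2 | any postbaseline PCS value | abnormal baseline and a postbaseline assessment |
| Weight, SAP 3.8.3.2 | PCS weight change at any postbaseline visit | Safety Population with a postbaseline value |
| Protocol 14.6 | PCS criteria met at any postbaseline visit | no baseline restriction stated |

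**2. Vital signs.** Take a baseline systolic pressure of 120 and a later value of 88. Then 88 is at or below 90, and the fall is 120 − 88 = 32, which is at least 20. The value is PCS, but a subject with a non-abnormal baseline is in neither numerator nor denominator.

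Suppose *abnormal* means already at the Table 7 limit in the same direction. The value needed to count in that direction is the limit moved by the required change:

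| Parameter | Low side | High side |
|---|---|---|
| Systolic (mm Hg) | 90 − 20 = 70 or below | 180 + 20 = 200 or above |
| Diastolic (mm Hg) | 50 − 15 = 35 or below | 105 + 15 = 120 or above |
| Heart rate (bpm) | 50 − 15 = 35 or below | 120 + 15 = 135 or above |

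If *abnormal* means outside a reference range, the size cannot be computed, because no range is given.

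**3. Labs, read literally.** Let D be the abnormal-baseline subjects with a postbaseline value, A those among D with a postbaseline PCS value, and N the subjects without an abnormal baseline who have a postbaseline PCS value. The stated ratio is (A + N)/D.

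- It exceeds 100% exactly when N > D − A, that is, when new cases from outside D outnumber the abnormal-baseline subjects who never become PCS.
- It is undefined when D = 0.

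**4. Labs, numerator matched as for vital signs.** The ratio becomes A/D, and all N cases drop out. Suppose *abnormal* means not in the Normal category of SAP Tables 4 and 5:

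- HDL: normal is 40 mg/dL or above and PCS is below 40. The denominator is exactly the subjects already PCS at baseline, so no new case can count.
- HbA1c: normal is below 5.7% and PCS is 5.7% or above. The result is the same.
- Prolactin at or above 1×ULN (30 ng/mL for females, 20 for males): the result is the same if *abnormal* means at or above ULN.
- HDL decrease of at least 20 mg/dL: a baseline below 40 less at least 20 gives a value below 20, so only those falls count.
- Total cholesterol, LDL, triglycerides and high fasting glucose: borderline or impaired baselines can still become newly PCS, but normal baselines cannot.

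**5. Scope.** SAP Table 3 has 34 criterion rows for 23 analytes. Five rows are change-only (total cholesterol, HDL, LDL, fasting glucose, triglycerides). Six are two-sided (random glucose, fasting glucose, potassium, sodium, platelets, leukocytes). SAP Tables 4 to 6 cover nine analytes: total cholesterol, LDL, HDL, triglycerides, glucose, HbA1c, ALT, AST and bilirubin. That leaves 23 − 9 = 14 without an SAP shift table, including all hematology, prolactin, creatine kinase, creatinine and electrolytes. No shift table covers vital signs.

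**The case against.** The strongest reply is that this is a slip of wording with little consequence. Parts of it stand.

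- **Intent.** The word is probably wrong, and the dataset specifications, programming specifications and mock tables, all separate documents, may already have it right. But it appears in three sentences across two sections, one of them written to define a numerator. The possible intentions (normal baseline, non-PCS baseline, everyone assessed) give different denominators, and the SAP does not choose.
- **Importance.** PCS labs and vital signs are not among the endpoints in Protocol 13.1, which lists adverse events, weight and waist circumference. Weight PCS is unaffected, and no test depends on these percentages. This limits the severity.
- **Other outputs.** The number of subjects with PCS labs carries no baseline restriction. SAP 3.8.3.1 also first promises a number of PCS vital-sign subjects without restriction, so that count survives unless the later numerator sentence governs it. Listings hold all cases, and the synopsis mentions lab shifts without limiting the analytes. Clinically significant labs are recorded as adverse events, and the general adverse-event definition in Protocol 13.2 can also capture vital-sign changes. None of these supplies the planned percentage. By-visit minima and maxima exclude unscheduled and repeat values, which SAP section 7 admits only to the PCS analyses and listings.
- **Undeclared change.** Protocol 14.6 names no denominator and Protocol 14.2 leaves detail to the SAP, so the absence of an entry in SAP section 5 is a secondary point.
- **New cases.** If *abnormal* means outside a reference range, a subject who is abnormal but not PCS at baseline and then becomes PCS is still counted. The loss is of subjects with a non-abnormal baseline.

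**Conclusion.** The concern holds and should be fixed. As written, the vital-sign percentage omits every subject with a non-abnormal baseline who becomes PCS. The lab percentage is either not a proportion (literal reading) or has the same omission (matched numerator). The problem is strongest for vital signs, where both halves are restricted and no shift table exists.

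The number of subjects affected cannot be given without assumed event rates, and none is assumed. The Table 7 limits and the HDL, HbA1c and prolactin results each depend on the stated reading of *abnormal*. The mismatch between lab numerator and denominator, and the exclusion for vital signs, follow from the text on any reading under which some subjects have a non-abnormal baseline. The data are not lost; the defect is in the specified summary.

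**What to change.** Replace the one sentence in SAP 3.8.2 and the two in SAP 3.8.3.1 so that numerator and denominator use one group.

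- **Default, for labs (threshold and change-only criteria) and vital signs.** Denominator: all Safety Population subjects with a baseline and at least one postbaseline value. Numerator: those among them with at least one postbaseline PCS value. This follows the protocol's plan. It mixes persisting with new cases for threshold criteria and leaves out subjects with no baseline value, so the table should state both facts.
- **Acceptable alternative for threshold criteria.** Use subjects whose baseline does not meet the criterion concerned (for vital signs, the observed-value part of SAP Table 7). Apply it separately to the low and high sides, so that a low baseline does not remove a subject from the high-side count; this affects the six two-sided rows of SAP Table 3 as well as vital signs. Record it in SAP section 5.

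Under either option, keep subjects already beyond a threshold at baseline in the listings.

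The default costs three replaced sentences and a denominator flag in programming, with no new data. The alternative adds a baseline flag per criterion and side, and one line in SAP section 5.

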3.8.3.2. Weight and Body Mass Index

Weight (kg), BMI (kg/m^2) and waist circumferences (cm) (baseline and change from baseline) will be summarized using observed data. Absolute and percent change from baseline in body weight will be summarized.

Number and percentage of subjects with $\geq 7\%$ or $\geq 10\%$ weight gain from baseline based on the observed data will be summarized by visit. Subgroup analysis by region (US vs non-US) will be performed. In addition, number and percentage of subjects with weight change values considered as PCS occurring at any post-baseline visit will be summarized. Criteria for PCS are presented below in [Table 8](#). The percentages will be calculated relative to the number of subjects in the Safety Population with at least one post-baseline value. A supportive listing will be provided for subjects with PCS values.

Table 8: Criteria for Potentially Clinically Significant (PCS) Changes from Baseline in Body Weight

Parameter	Criteria
Body Weight	Decrease from Baseline $\geq 7\%$ Increase from Baseline $\geq 7\%$

3.8.4. Columbia-Suicide Severity Rating Scale (C-SSRS)

The C-SSRS is a questionnaire used to measure the presence and intensity of suicidal ideation and behavior ([Table 9](#)).

Suicidal behavior and suicidal ideation will be summarized for the Safety Population. The number of subjects with suicidal ideation and suicidal behavior will be summarized when applicable.

Supportive tabular display of subjects with all values will be provided.

Table 9: C-SSRS Categories for Analysis

Category	C-SSRS Item response is “YES”
Suicidal behavior ^a	Preparatory acts or behavior Aborted attempt Interrupted attempt Actual attempt Complete suicide
Suicidal ideation ^a	Wish to be dead Non-specific active suicidal thoughts Active suicidal ideation with any methods (not plan) without intent to act Active suicidal ideation with some intent to act, without specific plan Active suicidal ideation with specific plan and intent
Non-Suicidal Self-Injurious Behavior	Non-Suicidal Self-Injurious Behavior

^a Derived based on responses to individual items listed within the category

3.9. Pharmacokinetic/ Pharmacodynamic Data Analysis

Not applicable.

4. INTERIM ANALYSES

As described in [Section 1](#), this SAP document is an update of the interim analysis that was conducted to support the ALKS 3831 New Drug Application (NDA). The full study population will be analyzed once the study is completed.

5. CHANGES IN CONDUCT OR PLANNED ANALYSES FROM THE PROTOCOL

To further assess the long-term durability, the following analysis was added in ISAP but was not specified in protocol:

- Shift analysis in CGI-S

6. DEFINITIONS AND CONVENTIONS FOR HANDLING OF THE DATA

Dataset specifications will be provided in a separate document.

6.1. Analysis Visit Windows

Scheduled analysis visits are visits at scheduled timepoints as specified in the protocol ([Table 1](#)).

Scheduled analysis visits during the study period will be the same as the nominal visits collected in eCRF. There will be one valid value of assessment kept for each scheduled analysis visit in summary/analysis statistics.

Unscheduled visits are visits with data not collected on the scheduled time point. Unscheduled visits will not be used for by-visit summary/analysis statistics, unless specified otherwise.

All unscheduled visits as collected in eCRF will be included in listings.

Last postbaseline values are defined as the last valid postbaseline values collected for each subject during the treatment period.

An early termination (ET) visit during the on-treatment period can be mapped to a scheduled visit, if there is no valid value already at that visit. Visit window as defined in [Table 10](#) for weight, waist circumference and CGI-S data and [Table 11](#) for vital signs, lab and IWQOL-Lite data will be used to map the assessments collected after premature discontinuation of the study drug. An ET visit that is not mapped will not be summarized in the tables or figures but will be included in the listing.

Table 10: Visit Window Definition for Weight, Waist Circumference and CGI-S Data

Analysis Visit to be Mapped to	Target Study Month	Target Visit Date	Visit Window
Visit 2	Month 1	Day 29	[2, 42]
Visit 3	Month 2	Day 57	[43, 70]
Visit 4	Month 3	Day 85	[71, 98]
Visit 5	Month 4	Day 113	[99, 126]
Visit 6	Month 5	Day 141	[127, 154]
Visit 7	Month 6	Day 169	[155, 182]
Visit 8	Month 7	Day 197	[183, 210]
Visit 9	Month 8	Day 225	[211, 238]
Visit 10	Month 9	Day 253	[239, 266]
Visit 11	Month 10	Day 281	[267, 294]
Visit 12	Month 11	Day 309	[295, 322]
Visit 13	Month 12	Day 337	[323, 350]
Visit 14	Month 13	Day 365	[351, 378]
Visit 15	Month 14	Day 393	[379, 406]
Visit 16	Month 15	Day 421	[407, 434]
Visit 17	Month 16	Day 449	[435, 462]

Analysis Visit to be Mapped to	Target Study Month	Target Visit Date	Visit Window
Visit 18	Month 17	Day 477	[463, 490]
Visit 19	Month 18	Day 505	[491, 518]
Visit 20	Month 19	Day 533	[519, 546]
Visit 21	Month 20	Day 561	[547, 574]
Visit 22	Month 21	Day 589	[575, 602]
Visit 23	Month 22	Day 617	[603, 630]
Visit 24	Month 23	Day 645	[631, 658]
Visit 25	Month 24	Day 673	[659, 686]
Visit 26	Month 25	Day 701	[687, 714]
Visit 27	Month 26	Day 729	[715, 742]
Visit 28	Month 27	Day 757	[743, 770]
Visit 29	Month 28	Day 785	[771, 798]
Visit 30	Month 29	Day 813	[799, 826]
Visit 31	Month 30	Day 841	[827, 854]
Visit 32	Month 31	Day 869	[855, 882]
Visit 33	Month 32	Day 897	[883, 910]
Visit 34	Month 33	Day 925	[911, 938]
Visit 35	Month 34	Day 953	[939, 966]
Visit 36	Month 35	Day 981	[967, 994]
Visit 37	Month 36	Day 1009	[995, 1022]
Visit 38	Month 37	Day 1037	[1023, 1050]
Visit 39	Month 38	Day 1065	[1051, 1078]
Visit 40	Month 39	Day 1093	[1079, 1106]
Visit 41	Month 40	Day 1121	[1107, 1134]
Visit 42	Month 41	Day 1149	[1135, 1162]
Visit 43	Month 42	Day 1177	[1163, 1190]
Visit 44	Month 43	Day 1205	[1191, 1218]
Visit 45	Month 44	Day 1233	[1219, 1246]
Visit 46	Month 45	Day 1261	[1247, 1274]
Visit 47	Month 46	Day 1289	[1275, 1302]
Visit 48	Month 47	Day 1317	[1303, 1330]

Analysis Visit to be Mapped to	Target Study Month	Target Visit Date	Visit Window
Visit 49	Month 48	Day 1345	[1331, 1351]

Visit Day is calculated as visit date – date of the first dose of study drug + 1. 1 month=28 days

Table 11: Visit Window Definition for Vital Signs, Lab and IWQOL-Lite Data

Analysis Visit to be Mapped to	Target Study Month	Target Visit Day	Visit Window
Visit 4	Month 3	Day 85	[2, 126]
Visit 7	Month 6	Day 169	[127, 210]
Visit 10	Month 9	Day 253	[211, 294]
Visit 13	Month 12	Day 337	[295, 378]
Visit 16	Month 15	Day 421	[379, 462]
Visit 19	Month 18	Day 505	[463, 546]
Visit 22	Month 21	Day 589	[547,630]
Visit 25	Month 24	Day 673	[631,714]
Visit 28	Month 27	Day 757	[715,798]
Visit 31	Month 30	Day 841	[799, 882]
Visit 34	Month 33	Day 925	[883,966]
Visit 37	Month 36	Day 1009	[967,1050]
Visit 40	Month 39	Day 1093	[1051,1134]
Visit 43	Month 42	Day 1177	[1135,1218]
Visit 46	Month 45	Day 1261	[1219,1302]
Visit 49	Month 48	Day 1345	[1303,1351]

Visit Day is calculated as visit date – date of the first dose of study drug + 1. 1 month=28 days

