7.3. Subject Withdrawal

A subject may be discontinued from the study at any time if the subject, Investigator, or Sponsor determines that it is not in the best interest of the subject to continue participation. If a subject has an absolute neutrophil count (ANC) $< 1.0 \times 10^3$ per μ L or Hemoglobin A1c (HbA1c) $\ge 6.5\%$ at any time, the PI (or designee) should discontinue the subject from participation immediately. Reasons for discontinuation include:

- Adverse Event
- Lack of Efficacy
- Lost to Follow-up
- Withdrawal by Subject
- Protocol Deviation (including non-compliance with study drug or study procedures)
- Pregnancy
- Study Terminated by Sponsor
- Other

If a subject withdraws from the study for any reason, any ongoing AEs will be followed until resolution, until deemed stable by the Investigator, or until the subject is deemed by the Investigator to be lost to follow-up. If, in the opinion of the Investigator, it is necessary to monitor a subject beyond the safety follow-up visit, the follow-up period may be extended as necessary. In such instances, the Sponsor and Investigator will agree to an acceptable follow-up schedule.

In the event that a subject chooses to withdraw from the study, the Investigator should make a reasonable effort to ascertain the reason(s) for withdrawal, while fully respecting the subject's rights. Subjects who terminate the treatment early (prior to Visit 25) will complete an early termination (ET) visit and the 4-week Safety Follow-up period. The ET visit should be scheduled as close as possible to the subject's last dose and will mimic the assessments scheduled to be conducted at the EOT Visit. If the subject fails or refuses to return to the study center, an attempt must be made to contact the subject by telephone in order to assess as many safety and efficacy parameters as possible. All data collected over the telephone must be documented and kept in the subject's record.

The Investigator must maintain a record of all subjects who fail to complete the study. The reason for study discontinuation will be documented and made on the appropriate electronic case report form (eCRF). If a subject is lost to follow-up, a reasonable attempt to contact the subject must be made and documented.

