14.6. Safety and Tolerability Analyses

All safety assessments will be summarized using descriptive statistics. All safety analyses will be based on observed data only, and no missing values will be imputed. Safety will be evaluated based on the occurrence of AEs (including clinically significant abnormal ECG findings), vital signs, and results of clinical laboratory tests. Reported AE terms will be coded using the MedDRA preferred terms and system organ classes.

Treatment-emergent AEs (TEAEs) are defined as AEs that occur or worsen after the first dose of study drug.

The summary tables will include the number and percent of subjects with TEAEs by system organ class, and by preferred terms within each system organ class. All SAEs, TEAEs leading to discontinuation, as well as additional categories of AEs as defined in the SAP will be summarized. The number and percentage of subjects with TEAEs will also be summarized by severity and by relationship to the study drug.

Observed values and change from baseline in laboratory parameters and vital signs will be summarized by visit.

The number and percentage of subjects who have met potentially clinically significant criteria at any postbaseline visit will be summarized for laboratory and vital signs. Supporting listings will be provided.

The number and percentage of subjects with C-SSRS assessments of suicidal ideation and behavior will also be summarized.

Concomitant medications will be summarized by World Health Organization (WHO) Anatomical Therapeutic Chemical (ATC) classification system. Listings will be provided for all concomitant medications.

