7. GENERAL STATISTICAL METHODOLOGY (AND REPORTING OF RESULTS)

In general, summary statistics (n, mean, SD, median, minimum, and maximum for continuous variables, and number and percentage of subjects in each category for categorical variables) will be provided. All summary tables will be based on observed data, and missing values will not be imputed, unless otherwise indicated. Measurements collected from unscheduled visits or repeated assessments will not be included in the by-visit summary tables or figures but will be included in the analyses for the PCS postbaseline values, and subject listings. Source data for the summary tables will be presented as subject data listings.

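### SAP 6.1, read literally, keeps unmapped early-termination values out of the ever-met PCS counts, in conflict with Protocol 14.6 and SAP 3.8.2, 3.8.3.2 and 7

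*SAP*

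**What the plan says.** **ET visits.** Protocol 7.3 requires an ET visit from subjects who stop treatment before Visit 25, close to the last dose, and says that it "will mimic the assessments scheduled to be conducted at the EOT Visit". Protocol Table 3 gives EOT/ET its own column, with laboratory samples, vital signs and weight. SAP 6.1 says that an ET visit in the on-treatment period "can be mapped to a scheduled visit, if there is no valid value already at that visit", using the windows of Table 10 (weight, waist circumference, CGI-S) or Table 11 (vital signs, laboratory, IWQOL-Lite). It then adds: "An ET visit that is not mapped will not be summarized in the tables or figures but will be included in the listing".

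**Unscheduled visits.** The same section gives the definition "Unscheduled visits are visits with data not collected on the scheduled time point" and bars these visits from by-visit summaries only. SAP Section 7 repeats that by-visit limit for unscheduled and repeat measurements and says that they "will be included in the analyses for the PCS postbaseline values, and subject listings".

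**PCS counts.**
- Protocol 14.6: the number and percentage of subjects who "met potentially clinically significant criteria at any postbaseline visit will be summarized for laboratory and vital signs".
- SAP 3.8.2: laboratory values are judged against the PCS criteria whether they come from scheduled or unscheduled visits.
- SAP 3.8.3.1: the vital-sign numerator needs at least one postbaseline PCS value.
- SAP 3.8.3.2: subjects with "weight change values considered as PCS occurring at any post-baseline visit will be summarized".

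SAP Section 5 lists one change from the protocol, the CGI-S shift analysis.

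**The concern.** Keeping one value per visit slot makes sense for by-visit means. It serves no purpose for a count of subjects who ever crossed a threshold. Yet the sentence on unmapped ET visits has no by-visit limit, while both sentences on unscheduled data have one. A programmer who follows 6.1 to the letter would count an abnormal value from an unscheduled visit as PCS, but not the value taken when the subject stops, if the window's scheduled visit had already supplied one.

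Removing values from an ever-met count can only lower it or leave it unchanged, so any error is in the favourable direction. Long-term safety is part of the primary objective. Two programmers could produce different PCS tables from this SAP, and the narrower version would be a departure from Protocol 14.6 that SAP Section 5 does not declare.

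**Working it through.** The documents give no share of unmapped ET visits, so there is no stated figure to reproduce. The size follows from the visit windows plus assumptions about timing.

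**Inputs from the documents**
- Target day = 1 + 28 × month (SAP Tables 10 and 11).
- Table 10 typical window: 14 days before target to 13 days after, 28 days in all. First window: Days 2–42.
- Table 11 typical window: 42 days before target to 41 days after, 84 days in all. First window: Days 2–126.
- ET applies before Visit 25, whose target is Day 673 (Protocol 7.3; SAP Tables 10 and 11), so ET days run from 2 to 672, which is 671 days.
- Scheduled visits may vary by ±4 days (Protocol Table 3).

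**Rule.** An ET visit is unmapped when it falls in a window after that window's scheduled visit has given a valid value. With every visit attended on its target day, these are the post-target days of each window.

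**Share within one window, ET day uniform**
- Weight: typical 13/28 = 46.4%; first window 13/41 = 31.7%.
- Laboratory and vital signs: typical 41/84 = 48.8%; first window 41/125 = 32.8%.

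**Share over Days 2–672, ET day uniform**
- Weight: Visits 2–24 give 23 windows × 13 = 299 days. Days 659–672 belong to the Visit 25 window and precede its target, so they add none. 299/671 = 44.6%.
- Laboratory and vital signs: Visits 4–22 give 7 windows × 41 = 287 days. Days 631–672 precede the Visit 25 target and add none. 287/671 = 42.8%.

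**Sensitivity to assumed timing** (simulation to Day 672, with ±4-day visits where visit timing matters)

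| Assumed pattern | Weight | Laboratory, vital signs |
|---|---|---|
| Uniform, all visits attended | 44.5% | 42.9% |
| Uniform, 10% of visits missed | 40.3% | 38.6% |
| Uniform, 20% missed | 35.8% | 34.3% |
| Exponential stopping, mean 400 days | 43.3% | 39.5% |
| Exponential stopping, mean 100 days | 37.7% | 25.5% |
| ET replaces the next monthly visit | 0% | 29.3% |
| The same, 20% missed | 0% | 23.3% |

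Taking the single-window figures as the upper ends, the range is 0–46% for weight and about 23–49% for laboratory tests and vital signs.

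**Effect of the fix.** If on-treatment ET values enter the PCS counts whether mapped or not, the excluded share of on-treatment ET visits is 0%. By-visit tables do not change.

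**The case against.** The strongest reply is that the PCS-specific text already includes these values. An unmapped ET visit can be read as meeting the 6.1 definition of an unscheduled visit, and Section 7 would then admit it. If it is instead a scheduled visit because it has a column in Protocol Table 3, SAP 3.8.2 covers its laboratory values anyway. Protocol 14.6 and SAP 3.8.3.2 speak of any postbaseline visit. The contrary sentence sits in a section about visit windows, where a by-visit meaning is natural; the same section defines the last postbaseline value without requiring that it be mapped. Dataset and programming specifications are held in separate documents.

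This stands to the extent that the SAP conflicts with itself rather than clearly barring ET values. It does not remove the conflict, because the SAP does not classify ET for this purpose and the sentence is unqualified.

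Two further replies also stand:
- A subject with another PCS value is counted regardless. With visits on target, an unmapped ET weight comes at most 13 days after a weight already counted. As SAP 3.8.2 and 3.8.3.1 are written, laboratory and vital-sign percentages also use only subjects with abnormal baseline values.
- A reader might infer that shift Tables 4–6 lose ET values while keeping unscheduled ones. The documents do not support that. SAP 3.8.2 limits laboratory summaries to scheduled values unless specified otherwise, and Section 7 makes its exception for PCS only. Unscheduled values therefore appear to be left out too, despite table titles that refer to any postbaseline value.

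**Conclusion.** The inconsistency is real and worth correcting. As written, 6.1 leaves unmapped ET values out of the PCS counts, while Protocol 14.6 and SAP 3.8.2, 3.8.3.2 and 7 point to inclusion. For ET visits before Visit 25, about 43% (laboratory, vital signs) and 45% (weight) would be unmapped if visits are attended on target and ET days are uniform. Across the other assumed patterns the ranges are about 23–49% and 0–46%. These are shares of ET visits. The number of subjects whose PCS status would change is unknown and smaller.

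Stronger readings are tempting but unsupported:
- That close to half of ET values cannot count as PCS. Counting through Visits 46 and 48 gives 15 × 41 = 615 of 1,301 days (47%) for laboratory tests and vital signs, and 47 × 13 = 611 of 1,329 (46%) for weight. Those figures run past the Visit 25 limit in Protocol 7.3 and still assume uniform timing and full attendance.
- That some definite number of assessments is lost. The documents give no number of early stoppers, so any such count rests on assumed dropout.
- That ET values are the most likely to be abnormal. This is plausible but not shown. A value that triggers stopping may come from an earlier sample that is already counted.

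**What to change.** - **SAP 6.1:** limit the sentence on unmapped ET visits to by-visit summaries.
- **SAP Section 7:** state that on-treatment ET values, mapped or not, enter all PCS counts alongside unscheduled and repeat values. Define on-treatment for this purpose, since 6.1 uses the term without defining it for ET mapping.
- **SAP Tables 4–6:** state one rule that treats unmapped ET and unscheduled values alike, preferably including both so that the tables match their titles.

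The cost is a few sentences and minor reprogramming. No new data are needed and the by-visit tables stay as they are. PCS percentages may come out slightly less favourable.
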